9. STATISTICAL CONSIDERATIONS

9.1 Sample Size Determination

The sample size in this study is calculated based on the non-inferiority hypothesis of the immune response to sIPV, taking the combination vaccination group as the test group and staggered vaccination group as the control group. The sample size calculation parameters are as follows: 1) The seroconversion rate of the control group is estimated as 90% referring to the previous clinical data of sIPV; 2) The non-inferiority criterion is: the lower limit of 95% CI of the difference between groups (test group-control group) $>-10\%$; 3) the allocation ratio between test group and control group for immunogenicity evaluation against either polio of three serotypes is 1:1; 4) the one-sided significance level is 0.025; 5) the overall statistical power ($1-\beta$) is 80%, with a corrected statistical power of 93.3% ($1-\beta/3$) for statistical test of each serotype. The sample size calculated using PASS 2022(V22.0.2) for each group is 233. Considering a dropout rate of approximately 15%, and a blood collection failure rate of approximately 10%, sample size of 360 is determined for each group.

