9.2 Analysis Sets

Analysis sets for immunogenicity evaluation

Full analysis set (FAS), following the principle of intent to treat (ITT), including all subjects who are randomized, **complete at least one vaccination against the antigen to be evaluated**, and have the valid immunogenicity results before the first vaccination. The participants who are vaccinated erroneously will be analyzed for the immunogenicity evaluation as randomized according to the ITT principle.

Per-protocol set (PPS), a subset of FAS, including all the subjects who are eligible for this study according to the inclusion and exclusion criteria, and then randomized, complete full vaccination as protocol specified, and have valid immunogenicity results before and after the vaccination. Subjects who meet the following conditions will be excluded from PPS:

- 1) Those who has significant protocol deviations;
- 2) Those who are vaccinated with the wrong vaccine;
- 3) Use of protocol prohibited vaccines or drugs
 - Other investigational or unlicensed products (drugs or vaccines)
 - Long-term use (lasting more than 14 days) of immunosuppressive or other immunomodulatory drugs (inhaled or topical steroids are allowed)
 - Immunoglobulin and/or blood preparations
- 4) Newly diagnosed autoimmune disease, including human immunodeficiency virus (HIV) infection
- 5) Other situations affecting the evaluation of vaccine immunogenicity

Analysis sets for safety evaluation

Safety Set (SS): All randomized subjects who completed at least one dose vaccination will be included in the safety set. Subjects who are vaccinated with the wrong vaccine will be analyzed for safety evaluation as treated according to ASaT principle (All Subjects as Treated).

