9.6 Method of Missing Data Handling

In immunogenicity analysis, the missing values in post-vaccination antibody data will be imputed by using the Last Observation Carried Forward (LOCF) method. The details in missing data handling will be described in the statistical analysis plan (SAP).

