4.3 Sample Size Consideration

The sample size in this study is calculated based on the non-inferiority hypothesis of the immune response to sIPV, taking the combination vaccination group as the test group and staggered vaccination group as the control group. The sample size calculation parameters are as follows:

- The seroconversion rate of the control group is estimated as 90% referring to the previous clinical data of sIPV;
- The non-inferiority criterion is: the lower limit of 95% Confidence Interval (CI) of the difference between groups (test group-control group) $>-10\%$;
- The allocation ratio between test group and control group for immunogenicity evaluation against either polio of three serotypes is 1:1;
- The one-sided significance level is 0.025;
- The overall statistical power ($1-\beta$) is 80%, with a corrected statistical power of 93.3% ($1-20\% / 3$) for statistical test of each serotype.

Considering the conditions above, the sample size calculated by using PASS 2022 (V22.0.2) for each group is 233. Considering a dropout rate of approximately 15% and a blood collection failure rate of approximately 10%, sample size of 360 is determined for each group.

5 Endpoints

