5.1 Immunogenicity Endpoints

➤ **In the comparison between group C1 and group S1**, the immunogenicity endpoints for neutralizing antibody (Nab) against polioviruses of serotype I, II, III at 28 days after last vaccination of sIPV will be defined as follows, respectively:

- (1) **Seroconversion (4-fold increase) rate**, which is defined as pre-vaccination Nab titer against polioviruses $<1:8$ and post-vaccination Nab titer against polioviruses $\geq 1:8$, or 4-fold Nab titer against polioviruses increase in case that pre-vaccination Nab titer against polioviruses $\geq 1:8$.
- (2) **Seroconversion Rate (SCR) in seronegative participants at pre-vaccination**, which is defined as pre-vaccination Nab titer against polioviruses $<1:8$ and post-vaccination Nab titer against polioviruses $\geq 1:8$.
- (3) **4-fold increase rate in seropositive participants at pre-vaccination**, which is defined as 4-fold Nab titer against polioviruses increase in case that pre-vaccination Nab titer against polioviruses $\geq 1:8$.
- (4) **Sero-Protection Rate (SPR)**, which is defined as Nab titer against polioviruses $\geq 1:8$.

(5) **Geometric Mean Titer (GMT) and Geometric Mean Fold Rise (GMFR)**, which is defined as the increase of Nab titers against polioviruses after vaccination compared to baseline.

(6) **GMT and GMFR in seronegative participants at pre-vaccination**

(7) **GMT and GMFR in seropositive participants at pre-vaccination**

➤ **In the comparison between group C2 and group S2**, the immunogenicity endpoints for Immunoglobulin G (IgG) antibody against Pertussis Toxin (PT), Filamentous Hemagglutinin (FHA) and Pertactin (PRN) at 28 days after last vaccination of DTP-HepB-Hib will be defined as follows, respectively:

- (1) **Seropositivity rate**, which is defined as IgG antibody concentration after vaccination ≥ 20 EU/ml.
- (2) **SCR**, which is defined as pre-vaccination IgG antibody concentration < 5 EU/ml and post-vaccination concentration ≥ 20 EU/ml, or 5 EU/ml \leq pre-vaccination IgG antibody concentration

<20 EU/ml and 4-fold concentration increase, or pre-vaccination IgG antibody concentration \geq 20 EU/ml and 2-fold concentration increase.

(3) Geometric Mean Concentration (GMC) and GMFR, which is defined as the increase of IgG antibody concentrations after vaccination compare to baseline.

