7.7 Immunogenicity Evaluation

➤ **Immunogenicity evaluation for Nab against polioviruses**

The following analysis will be performed for Nab against polioviruses of serotype I, II, III between **group C1 and group S1 at 28 days after last vaccination of sIPV**, respectively:

The seroconversion (4-fold increase) rate in all participants, SCR in seronegative participants at pre-vaccination, 4-fold increase rate in seropositive participants at pre-vaccination and SPR in all participants will be estimated in each group. Clopper Pearson method will be used to calculate 95% CIs and Cochran-Mantel-Haenszel- χ^2 (CMH- χ^2) test stratified by study site (including Bangladesh 01, Pakistan 01 and Pakistan 02) will be used to test the differences between the two groups. The CMH method will be used to calculate the rate difference between (group C1 - group S1) and 95% CIs. Non-inferiority will be concluded if the lower limit of the 95% CI of SCR difference between group C1 and Group S1 >-10%.

Analysis of covariance model will be modeled to analyze Nab level against polioviruses at 28 days after last vaccination of sIPV. In this model, the log-transformed Nab data against polioviruses at 28 days after last vaccination of sIPV will be included as dependent variable, the log-transformed Nab data before vaccination as a covariate, and treatment group (including C1 and S1) and study site (including Bangladesh 01, Pakistan 01 and Pakistan 02) are the fixed effect. From the model, the LS-adjusted log-transformed Nab level against polioviruses at 28 days after last vaccination of sIPV in each group and the difference between (group C1 - group S1) will be calculated. The adjusted GMT at 28 days after last vaccination of sIPV in each group, GMT ratio between (group C1/group S1), and its 95% CIs will be obtained after inverse log-transformation.

Descriptive statistics, including geometric mean and 95% CIs, for GMT and GMFR in all participants, seronegative participants at pre-vaccination and seropositive participants at pre-vaccination will be presented by groups. The group t-test after log-transformation will be used to compare the differences between groups. The ratio of GMT between groups and their 95% CIs will be estimated as well.

The forest plot of the post-vaccination seroconversion (4-fold increase) rate for all participants in comparison (group C1 and group S1) will be plotted.

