The reverse cumulative distribution plot of antibody titers at pre- and post-vaccination time points will be plotted.

The above analysis will be based on the FAS and PPS.

➤ **Immunogenicity evaluation for IgG antibodies against pertussis**

The following analysis will be performed for IgG antibodies against PT, FHA and PRN of **group C2 and group S2 at 28 days after last vaccination of DTP-HepB-Hib**, respectively:

The seropositivity rate and SCR for all participants will be estimated by groups. The Clopper Pearson method will be used to calculate 95% CIs and the CMH- χ^2 test considering the study site (including Bangladesh 01, Pakistan 01 and Pakistan 02) as a stratification factor will be used to test the differences between groups. The CMH- χ^2 method will be used to calculate the rate difference between (group C2 - group S2) and 95% CIs.

Analysis of covariance model will be modeled to analyze IgG antibody level against PT, FHA and PRN at 28 days after last vaccination of DTP-HepB-Hib. In this model, the log-transformed IgG antibody data against PT, FHA and PRN at 28 days after last vaccination of DTP-HepB-Hib will be included as dependent variable, the log-transformed IgG antibody data before vaccination as a covariate, and treatment group (including C2 and S2) and study site (including Bangladesh and Pakistan) are the fixed effect. From the model, the LS-adjusted log-transformed IgG antibody level against PT, FHA and PRN at 28 days after last vaccination of DTP-HepB-Hib in each group and the difference between (group C2 - group S2) will be calculated. The adjusted GMC at 28 days after last vaccination of DTP-HepB-Hib in each group, GMC ratio between (group C2/group S2), and its 95% CIs will be obtained after inverse log-transformation.

Descriptive statistics, including geometric mean and 95% CIs, for GMC and GMFR of all participants will be presented by groups. The grouped t-test after log-transformation will be used to compare the differences between groups. The ratio of GMC between groups and their 95% CIs will be estimated as well.

The reverse cumulative distribution plot of antibody concentrations at pre- and post-vaccination time points will be plotted.

The above analysis will be based on the FAS and PPS.

➤ **Immunogenicity evaluation for IgG antibodies against diphtheria, tetanus, HepB, Hib and pneumococcal**

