7.9 Handling of Missing Data

- The missing values of immunogenicity analysis in FAS will be imputed by using Last Observation Carried Forward (LOCF) method.
- The missing values of safety evaluation will not be imputed in this study.

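### The stated 93.3% and 80% power describe infants with both blood samples, not the FAS with LOCF, and neither document says which set decides the primary test

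*Protocol*

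**What the plan says.** Protocol 9.1 and SAP 4.3 size the polio comparison (C1 against S1) at 90% seroconversion, a 10-point margin and one-sided 0.025. Power is 93.3% per serotype, so that overall power is 80%. The result is 233 per group. Protocol 9.1 continues: "Considering a dropout rate of approximately 15%, and a blood collection failure rate of approximately 10%, sample size of 360 is determined". SAP 4.3 says the same: "Considering a dropout rate of approximately 15% and a blood collection failure rate of approximately 10%, sample size of 360 is determined". Neither section says which analysis set the power refers to, which blood draw the 10% covers, or how the two losses combine.

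The two immunogenicity sets treat a missing post-vaccination sample differently. Besides randomisation and one relevant dose, the FAS (Protocol 9.2, SAP 6) asks only that infants "have the valid immunogenicity results before the first vaccination". The PPS needs valid results both before and after vaccination.

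Protocol 9.6 states that "the missing values in post-vaccination antibody data will be imputed by using the Last Observation Carried Forward (LOCF) method" and leaves the detail to the SAP. SAP 7.9 adds only that this applies in the FAS: "The missing values of immunogenicity analysis in FAS will be imputed by using Last Observation Carried Forward (LOCF) method".

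The decision rule in SAP 7.7 reads "Non-inferiority will be concluded if the lower limit of the 95% CI of SCR difference between group C1 and Group S1" is above −10%, with no set named. The polio subsection closes with "The above analysis will be based on the FAS and PPS". Protocol 9.3.4 names no set either.

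**The concern.** Raising 233 to 360 treats lost infants as leaving the analysis while the rate stays at 90%. That fits a set restricted to infants with both samples. In the FAS, infants without a post-vaccination sample stay in the denominator. Blood is drawn only at baseline and once after the series (Protocol 4.1), so LOCF has only the baseline titre to carry. A carried baseline is a fold rise of 1. It cannot cross 1:8 from below, and it cannot meet the other arm of the definition, "or 4-fold Nab titer against polioviruses increase in case that pre-vaccination Nab titer against polioviruses" is at least 1:8. Each such infant is scored as a failure.

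Two things are at stake. First, the FAS test has less power than the plan states, and if FAS and PPS disagree the plan does not say which result stands. Second, adding the same share of automatic failures to both groups pulls the two rates together, which favours a conclusion of non-inferiority when co-administration is truly worse.

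**Working it through.** **Inputs.** From Protocol 9.1 and SAP 4.3: control rate 90%, margin 10 points, one-sided 0.025, 233 and 360 per group, 15% dropout, 10% blood-collection failure. Assumed: the same 90% in the test group, equal losses in both groups, and dropouts having no post-vaccination sample. Randomisation, baseline blood and first dose all fall at Visit 1 (Protocol 8.6), so an infant in C1 or S1 who drops out later remains in the FAS.

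**1. The plan's own figure.** The Farrington–Manning score formula is power = Φ[(0.10√n − 1.96·s0)/s1]. Here s1² = 2 × 0.90 × 0.10 = 0.18. The rates restricted to the margin are 0.8313 and 0.9313, so s0² = 0.8313 × 0.1687 + 0.9313 × 0.0687 = 0.204. At n = 233: (1.526 − 0.886)/0.424 = 1.51, giving 93.5%. The formula's required n is 232. The stated 233 and 93.3% reproduce. The 80% is the bound 1 − 3 × (0.20/3).

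**2. Infants with both samples.** Applying each loss once, 360 × 0.85 × 0.90 = 275, or 360 × 0.75 = 270. Power is 96–97% per serotype and about 91–92% overall, before PPS exclusions for deviations.

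**3. The FAS under LOCF.** With f the share of FAS infants who have a post-vaccination sample, the FAS rate is p = 0.90 × f in both groups. The normal approximation is power = Φ[0.10/√(2p(1−p)/n) − 1.96]. For the first row below: 2 × 0.765 × 0.235/324 = 0.00111, square root 0.0333, and 0.10/0.0333 − 1.96 = 1.04, giving 85.1%.

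| Losses | FAS n | f | p | Normal approx. | Score | All three serotypes |
|---|---|---|---|---|---|---|
| 15% dropout; 10% at baseline draw (leaves FAS) | 324 | 0.85 | 0.765 | 85.1% | 85% | 71% |
| 15% dropout; 10% at post draw, compounded | 360 | 0.765 | 0.6885 | 82.6% | 83% | 69% |
| 15% dropout; 10% at post draw, added | 360 | 0.75 | 0.675 | 81.7% | 82% | 68% |
| 15% dropout only | 360 | 0.85 | 0.765 | 88.6% | 88% | 77% |

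The last column comes from 100,000 simulated trials, with loss shared across serotypes and conversion otherwise independent. The documents give no between-serotype correlation. The plan's own bound, 1 − 3(1 − power), would give lower values: 55%, 48%, 46% and 65% in row order.

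**4. Loss the FAS can absorb.** Setting the power in step 3 to 93.3% at n = 360 gives f = 0.906 (0.910 by the score formula), a retained loss of about 9%.

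**5. Higher response.** Protocol 2.2.2.1 reports 98.6–99.6% in an earlier trial, adjusted for maternal antibody. At 98.6% and 99.5%, simulated overall FAS power is 90% and 92% (row 1), 83% and 86% (row 2), 82% and 85% (row 3), and 93% and 95% (row 4). Per-serotype power in rows 2 and 3 stays at 86–88%.

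**6. A true deficit at the margin.** With true rates of 80% and 90%, the FAS difference is −0.10 × f. The chance of concluding non-inferiority for that serotype is Φ[(0.10 − 0.10f)/SE − 1.96].
- Row 1: FAS rates 0.680 and 0.765, SE 0.0350, 0.015/0.0350 − 1.96 = −1.53, giving 6.3%.
- Row 2: 0.612 and 0.6885, SE 0.0354, giving 9.7%.
- Row 3: 0.600 and 0.675, SE 0.0357, giving 10.4%.
- Row 4: 0.680 and 0.765, SE 0.0332, giving 6.6%.

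The nominal value is 2.5%.

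**The case against.** **Response may well exceed 90%.** This stands in part. At 98.6–99.5%, overall FAS power is above 80% in every row. Per-serotype power still misses 93.3% when the 10% falls at the post-vaccination draw, and the unnamed deciding set remains a gap at any response rate.

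**Dropout need not mean no sample.** The documents do not define it. Infants barred from further doses may continue other procedures (Protocol 5.3), and those who miss a visit continue to later ones (Protocol 6.4). If retained loss is about 9% or less, the FAS also meets the per-serotype target. The plan itself budgets 15%.

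**Denominators use participants with data.** Protocol 9.3.1 and SAP 7.1.1 say so as a general rule, but SAP 7.9 gives a specific rule for the FAS, and an imputed value is no longer missing.

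A reader might infer more than the documents support:
- *That the 10% applies at each of two draws.* Then 233/0.65 = 359, close to 360, and FAS power falls to 76–79% per serotype and 61–63% overall. The documents state the 10% once and never say it applies twice. Applied once, the losses give 233/(0.85 × 0.90) = 305 or 233/0.75 = 311. How 360 was reached is unexplained, but it is not shown to be wrong.
- *That the stated power holds only for the PPS, or that the trial is too small.* The PPS also removes deviations, which are not separately budgeted. On the single-loss reading, 360 leaves 37 to 42 infants per group above 233 with both samples.
- *That the PPS must decide.* Naming either set, or requiring both, would close the gap.

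**Conclusion.** The point holds in a limited form. The figures 233, 93.3% and 80% describe infants with both samples. Under the plan's own inputs they do not describe the FAS, where power is about 82–88% per serotype and 68–77% overall. These values assume 90% response among sampled infants, equal losses in both groups, dropouts without a post-vaccination sample, and the 10% applied once or not at all. The overall figure also depends on the unstated correlation between serotypes. It is an expected loss of power in one of two tested sets, and it narrows or disappears if response is higher or losses are lower.

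The inflated chance of a false conclusion, about 6–10% per serotype at a true 80% against 90%, arises from the same rule and matters if the FAS has any deciding role. That LOCF carries the baseline titre is inferred from the sampling schedule, but the plan provides no other earlier value.

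**What to change.** Before database lock, which SAP 2.1 already sets as the deadline for a final SAP:

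1. In SAP 7.7 and Protocol 9.3.4, state whether hypothesis test I must succeed in the PPS, the FAS or both.
2. In Protocol 9.1 and SAP 4.3, say that 233, 93.3% and 80% refer to infants with both samples. State which draw the 10% covers and how the losses lead to 360. If the FAS has a deciding role, quote its own power.
3. In SAP 7.9 and Protocol 9.6, do not use baseline-carried LOCF for the seroconversion non-inferiority test. Analyse FAS infants with a valid post-vaccination result, or use multiple imputation, and state the missing-data assumption. Keep missing-as-failure as a sensitivity analysis only.

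The cost is a short SAP revision, a protocol amendment and a little more analysis. If the FAS has a deciding role, the stated power may be less favourable. No extra infants are needed.

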9.2 Analysis Sets

Analysis sets for immunogenicity evaluation

Full analysis set (FAS), following the principle of intent to treat (ITT), including all subjects who are randomized, **complete at least one vaccination against the antigen to be evaluated**, and have the valid immunogenicity results before the first vaccination. The participants who are vaccinated erroneously will be analyzed for the immunogenicity evaluation as randomized according to the ITT principle.

Per-protocol set (PPS), a subset of FAS, including all the subjects who are eligible for this study according to the inclusion and exclusion criteria, and then randomized, complete full vaccination as protocol specified, and have valid immunogenicity results before and after the vaccination. Subjects who meet the following conditions will be excluded from PPS:

- 1) Those who has significant protocol deviations;
- 2) Those who are vaccinated with the wrong vaccine;
- 3) Use of protocol prohibited vaccines or drugs
 - Other investigational or unlicensed products (drugs or vaccines)
 - Long-term use (lasting more than 14 days) of immunosuppressive or other immunomodulatory drugs (inhaled or topical steroids are allowed)
 - Immunoglobulin and/or blood preparations
- 4) Newly diagnosed autoimmune disease, including human immunodeficiency virus (HIV) infection
- 5) Other situations affecting the evaluation of vaccine immunogenicity

Analysis sets for safety evaluation

Safety Set (SS): All randomized subjects who completed at least one dose vaccination will be included in the safety set. Subjects who are vaccinated with the wrong vaccine will be analyzed for safety evaluation as treated according to ASaT principle (All Subjects as Treated).

9.3 Statistical Methods

9.3.1 General Considerations

Unless otherwise stated, summary statistics including the number of participants, mean, standard deviation, median, minimum and maximum, will be presented for all continuous variables. For categorical variables, per category, the absolute counts (n) and percentages (%) of participants with data, and if appropriate, the number of patients with missing data, will be prepared.

All statistical analysis will be performed by using SAS 9.4 or later version.

9.3.2 Disposition of Participants

A summary of the analysis sets includes the number and percentage of participants for the following categories: participants screened, enrolled, numbers of subjects who complete each dose of vaccination, participants in each analysis set. The reasons for withdrawal for the participants who discontinue the study will be summarized as well. All results will be presented for each group.

A participant-level data listing of study completion information including the reason for screened failure and study discontinuation will be presented.

